7.1 Primary Safety Endpoints

Safety of intrathecal hydromorphone hydrochloride as assessed through collection of AEs and SAEs during the conduct of the trial. Particular attention will be paid to:

- The rate of confirmed granulomas verified by MRI (with and without contrast), CT myelogram or by surgery.
- The rate of suspected granulomas that cannot be verified by MRI (with and without contrast), CT myelogram or surgery.

7.2 Secondary Endpoints

The following Secondary Endpoints will be assessed. Each of these endpoints will be evaluated at each study visit.

- Change in the Visual Analog Scale Pain Intensity (VASPI) overtime.
- Change in the Brief Pain Inventory (BPI) overtime.
- Change in the Patient Global Impression of Change (PGIC) overtime.

8 Statistical Methods

8.1 Sample Size

This study is planned to enroll approximately 350 subjects at up to thirty (30) investigative sites to obtain 300 subjects completing 6-months and 100 subjects completing 12-months of intrathecal hydromorphone hydrochloride therapy. Additional subjects may be enrolled as deemed necessary to reach the study submission objectives for subjects on long term intrathecal hydromorphone hydrochloride therapy.

8.2 Randomization and Masking

This is an open-label, single-arm safety trial. As such there is no blinding. There is no randomization in this trial.

Each subject who is entered from the CNS-HYD201US study will retain their subject number from the previous study and carry that number into this trial.

Unique subjects enrolled directly into the CNS-HYD202US trial will be assigned a subject number consisting of a two-digit site number and three-digit sequential subject number (SS-XXX). This number will be used for the entire duration of the trial.

8.3 Subject Discontinuation and Replacement of Subjects

Subjects may withdraw from the study at any time. Subjects may be discontinued from study treatment or the study at the request of the Investigator or Sponsor.

Additional subjects may be enrolled as deemed necessary to reach the study submission objectives of 300 subjects completing 6 months and 100 subjects completing 12 months of intrathecal hydromorphone hydrochloride therapy.

8.4 Final Analysis and Reporting

Study submission objectives will be met when 300 subjects complete 6 months and 100 subjects complete 12 months of intrathecal hydromorphone therapy. For the purpose of the clinical study report, the analyses may occur any time after the study submission objectives are met. At the time of submission, some subjects may still be receiving study treatment. Therefore, any subsequent safety data collected on those subjects will be submitted via a safety update, unless other format is requested by Regulatory Authorities. Database lock will occur when all study submission objectives are met or subjects have completed the study (or discontinued early) and all data have been monitored. A business decision was made by Piramal to only perform the safety analysis of the study once all subjects had completed the study. Modules pertaining to the safety data were monitored, cleaned and queried, while modules pertaining to the efficacy endpoints (VASPI, BPI, PGIC) data were no longer cleaned or queried after 11 September 2017. The database was locked on 07 February 2018. Subsequently, Piramal made the business decision to move forward with the program and to complete the remaining analysis of the study. The remaining analyses will be performed under this version, Version 4.0 dated 04 February 2019 of the SAP, and will be performed on the previously locked data. No additional data cleaning will take place.

In addition, no database may be locked, or final analyses completed until the original version of the SAP had been approved. The final analyses outlined in the protocol and in this SAP will be carried out after:

- The SAP has been approved;
- The study database has been authorized by the sponsor clinical team as complete and final; and
- Protocol violations have been identified.

Further exploratory analyses not necessarily identified in this SAP may be performed to support the clinical development program. Any post-hoc or unplanned analyses performed and not identified in this SAP will be clearly identified in the CSR.

8.5 Handling of Missing Data

All missing data will remain missing and will not be imputed. Only observed data will be

summarized. The only exception is in the BPI total score as described in the corresponding section.

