14.0 STATISTICAL CONSIDERATIONS

14.1 Sample Size Determination

This study is planned to enroll approximately 350 subjects at up to thirty (30) investigative sites to obtain 300 subjects completing 6-months and 100 subjects completing 12-months of intrathecal hydromorphone hydrochloride therapy. Additional subjects may be enrolled as deemed necessary to reach the study completion requirements for subjects on long term intrathecal hydromorphone hydrochloride therapy.

Protocol CNS-HYD202US

Version: 7.0

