9.6 Secondary Endpoints

9.6.1 Visual Analogue Scale of Pain Intensity (VASPI)

The VASPI will be a single question assessing how severe a subject's pain is 'right now'.

Scoring is based on the continuous visual analog scale (measured in mm) ranging from no pain at the start of the scale to unbearable pain at the end of the scale. VASPI will be assessed at Baseline and each study visit, including the final visit. The VASPI scores, as well as change from baseline, will be summarized at each visit. All assessments will be listed.

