9.6.2 Brief Pain Inventory (BPI)

The BPI will consist of two domains, pain severity and pain interference with functioning.

Pain severity will be evaluated by rating pain on a scale from 0 (no pain) to 10 (pain as bad as you can imagine) for the 'worst', 'least', and 'average' pain experienced in the past 24 hours, as well as, the pain experienced 'now'. In addition, a calculated mean pain severity score will be based on the sum of all 4 of the pain scores divided by 4. If any of the 4 questions are missing, then the calculated mean pain severity score will be considered missing.

Pain interference with daily functioning will be evaluated by rating interference on a scale from 0 (does not interfere) to 10 (completely interferes) for 'general activity', 'mood', 'walking ability', 'normal work', 'relation with other people', 'sleep', and 'enjoyment of life'. A calculated mean pain interference will be based on the sum of non-missing interference questions answered divided by the number of questions answered. The mean should be set to missing if fewer than 4 pain interference questions are answered.

The BPI will be assessed at Baseline, Day 28, Day 80, Day 160, Day 286, and at the final visit. The BPI scores, as well as change from baseline, will be summarized at each specified visit for the following: pain severity 'worst', pain severity 'average', calculated mean pain severity, and calculated mean pain interference with function. All assessment, including the calculated mean scores, will be listed.

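### VASPI, BPI and PGIC are summarised by visit on observed data only, with no check on selective dropout and no rule for where early-termination scores go, so the trend over time could mislead

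*SAP*

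**What the plan says.** The secondary endpoints in Protocol 3.2.2 and SAP 7.2 are change over time in VASPI, BPI and PGIC. SAP 8.5 gives the general rule for missing data: "All missing data will remain missing and will not be imputed". It then adds: "The only exception is in the BPI total score as described in the corresponding section". SAP 9.6.2 defines no BPI total score. Its only allowance for partial data works at item level, on mean interference: "The mean should be set to missing if fewer than 4 pain interference questions are answered". That does nothing for a missed visit.

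For VASPI, SAP 9.6.1 says: "The VASPI scores, as well as change from baseline, will be summarized at each visit". For BPI, SAP 9.6.2 says: "The BPI scores, as well as change from baseline, will be summarized at each specified visit". SAP 9.6.3 summarises the PGIC score by visit in the same way. SAP 6 names the ITT population (all treated subjects) and repeats the analysis without Site 028. The table list in SAP Appendix A has no split by completion status, no longitudinal model and no sensitivity analysis for dropout.

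Protocol 9.5 holds the final visit at about Day 365 or at discontinuation for any reason. Protocol 11.0 asks for final-visit procedures in anyone who stops study drug early, and Protocol Appendix A lists VASPI, BPI and PGIC at that visit. The SAP refers to the final visit without distinguishing the two cases.

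**The concern.** A by-visit mean describes change over time only if the same kind of subject contributes at every visit. Here the contributors at Days 160, 216 and 286 are those who have not yet left. If those who leave were doing worse, the remaining means drift towards better scores even when nobody improves. No control arm shares the attrition and would reveal this. The ITT label gives no protection, because it fixes who is eligible and not who has a value.

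The last column has a separate problem. A subject who stops at, say, Day 120 has a final visit, and so does a subject who completes Day 365. If both enter one column, it cannot be read as a 12-month result. This will arise in practice: SAP Appendix B records that Site 028 was closed during the study and that its active subjects were brought in for final visits.

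At stake is the reading of a long-term pain trend that SAP 2 intends for regulatory submissions or manuscripts. The primary safety conclusion is not affected.

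**Working it through.** **Inputs from the documents.** Planned enrolment is 350, with completer targets of "300 subjects completing 6-months and 100 subjects completing 12-months" (Protocol 14.1). No dropout rate, SD, expected effect or power is stated, so there is no figure of the plan's own to reproduce. The 6-month target implies a loss of 1 − 300/350 = 14.3%. That is an enrolment target, which may be met by enrolling more subjects, and serves here only as an illustration.

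**Formula.** Let d be the fraction gone, S the stayers' mean change and L the mean change that leavers would have had (negative means less pain). The all-subject mean is (1 − d)S + dL. The observed mean is S. The error is S − [(1 − d)S + dL] = −d(L − S).

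**Numbers.** Assume that L − S is 10 to 30 mm; this is not in the documents.
- 14.3% gone: 0.143 × 10 to 30 = 1.4 to 4.3 mm too favourable.
- A constant rate (assumption) gives a 12-month loss of 1 − (300/350)² = 26.5%: 0.265 × 10 to 30 = 2.7 to 8.0 mm. This applies to a Day 365 column of completers only.
- Day 286, the last scheduled visit before the final one, lies between. Taking 6 months as 182.5 days, the loss is 1 − (300/350)^(286/182.5) = 21.5%, which gives 2.1 to 6.4 mm.
- L = S: zero.

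The same formula applies to BPI and PGIC on their own scales.

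**Does the mechanism matter?** I simulated 200,000 subjects on the protocol's visit days with no true mean change. Assumptions, none from the documents: VASPI mean 60 mm, SD 25, within-subject correlation 0.6, and logistic dropout with slope 0.5 to 1.0 per 25 mm. Dropout was driven by pain level or, in a second set of runs, by worsening from baseline, with an individual response SD of 15 mm. Entries are apparent effects in mm.

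| Loss by 12 months | Day 286 raw score, dropout by pain level | Day 286 change, dropout by pain level | Day 286 change, dropout by worsening | Final-visit change with early-termination values pooled, dropout by worsening |
|---|---|---|---|---|
| 14.3% | −1.0 to −1.8 | 0.0 to +0.2 | −1.1 to −2.3 | +0.8 to +1.3 |
| 25% | −1.9 to −3.4 | +0.1 to +0.3 | −2.2 to −4.0 | +1.2 to +2.3 |
| 40% | −3.3 to −5.6 | +0.2 to +0.5 | −3.8 to −6.8 | +1.9 to +3.4 |

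With slope 0 (dropout unrelated to pain), every entry is within 0.1 mm of zero. So change from baseline is materially biased only when dropout follows worsening. Dropout by pain level shifts the raw scores, which are also tabulated, and leaves change almost untouched. Pooling exit values reverses the sign, because leavers are measured at the moment they are doing badly. The planned tables cannot tell these cases apart.

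**The case against.** **Early leavers are measured.** Protocol 9.5 and 11.0 require their scores at exit. This stands and limits the point: their outcomes are collected and listed. But they are absent from the scheduled visits after they leave, and where their exit values are tabulated is undefined.

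**Selective loss is not shown.** A reader might infer that poor relief is a stated reason to stop and that pain will therefore appear to improve. The documents do not support either. Protocol 10.0 lists noncompliance, an unresolved significant safety event, loss to follow-up and withdrawn consent. Protocol 3.7 names granuloma and intolerable related events. Protocol 3.1 and 9.4 answer inadequate relief with dose adjustment, added intrathecal drugs and oral opioids. Selection remains plausible, because intolerable effects end treatment and SAP 8.3 lets subjects withdraw at any time.

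**The tables already expose attrition.** Each shows n (SAP 8.7), withdrawal reasons are tabulated (SAP 9.1) and all assessments are listed. True, but nothing links the reasons to the scores.

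**The study is descriptive.** No test is planned, and Protocol 8.0 says that there is no efficacy endpoint. This lowers the weight of the point. Even so, SAP 8.4 calls these measures efficacy endpoints.

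**A model is no cure.** It assumes missing at random, and it cannot isolate a drug effect while doses and co-medication vary freely. This stands. A reader might also conclude that any trend seen only in the observed tables must be attrition. That does not follow, since the two can differ because the model or its assumption is wrong.

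**Conclusion.** The concern holds in conditional form. The scheduled-visit summaries use observed data only, the later ones cover a shrinking set of subjects, and no planned analysis examines the effect of dropout. Whether the trend is in fact distorted cannot be known from the documents.

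The sizes above (1.4 to 4.3 mm and 2.7 to 8.0 mm) rest on an assumed 10 to 30 mm gap between leavers and stayers and on losses derived from a completer target. Under the simulation's assumptions, the Day 286 effect at 14.3% loss is smaller, about 1 to 2 mm.

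A reader might take the 12-month target as retention and compute 1 − 100/350 = 71.4% lost, hence 7.1 to 21.4 mm. That is not supported. SAP 8.4 makes the 100 a submission threshold that can be met while others are still on treatment, and SAP 2 indicates that all follow-up had ended before database lock.

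The undefined handling of early-termination values is the firmer gap, because it needs no assumption about who leaves. No error rate is at issue; the risk is over-reading a pattern over time.

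**What to change.** Keep the observed-case tables and add to SAP 9.6:

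1. Report Day 365 completers' values separately from early-termination values, not pooled in one final-visit column. State which visit, if any, an early-termination value takes in the model below.
2. Show VASPI, BPI and PGIC by visit for 12-month completers and for early leavers. Give each group's baseline mean, and the last observed change (last observed score for PGIC) by reason for withdrawal.
3. For VASPI and BPI, fit one supportive repeated-measures model with visit and baseline score and an unstructured covariance. Give mean change and a 95% CI per visit for all dosed subjects, in both ITT populations, for estimation only.
4. State that a trend seen only in the observed-case tables will not be interpreted as sustained benefit.

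The cost is SAP wording and two extra tables, from locked data and fields already collected. The downside is that the model assumes missing at random; the split in item 2 helps the reader judge that assumption.

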8.6 Interim Analysis

No formal interim analyses will be conducted. See section 8.4 of the SAP for further details regarding the timing of the analyses for study submission and the reporting of subsequent safety data.

8.7 Comments on Statistical Analysis

The following general comments apply to all statistical analyses and data presentations:

- Unless otherwise noted, tables will present summaries by formulation concentration (2 mg/mL and 10 mg/mL) and all subjects.
- Summaries will include frequency and percentages for categorical data and frequency, mean, standard deviation, median, minimum, and maximum for quantitative data.
- Duration variables will be calculated using the general formula: duration = (end date start date) + 1.
- Individual subject listings of all data represented on the eCRFs will be provided to facilitate the investigation of tabulated values and to allow for the clinical review of all data.
- Version 9.1 or greater of SAS statistical software package will be used to provide all summaries, listings, and graphs described in this document.
- All raw data will be presented to the original number of data places. The means and medians will be presented to one more decimal place than the raw data. The standard deviations will be presented to two more decimal places than the raw data. For averages of averages, the means and medians will also be presented to one more decimal place than the raw data and the standard deviations will also be presented to two more decimals places than the raw data.
- Generally, the denominator for percentages will be based on the number of subjects in the study population. However, for cases where appropriate, the denominator for percentages will be based on the number of subjects with non-missing data. Unless otherwise noted, all percentages will be presented to one decimal place.

9 Statistical Analyses

9.1 Subject Disposition

The number and percent of subjects in the Safety population will be summarized. The number and percent of subjects who enrolled in the study, completed the study, withdrew from the study and their reasons for withdrawal will also be tabulated. The number and percentage of subjects who rolled over from study CNS-HYD201US, subjects who were naïve to intrathecal opioids, and those who had prior opioid treatment will also be summarized. Subject disposition will be summarized using all enrolled subjects. Enrolled subjects will be those subjects who signed the informed consent form.

A listing summarizing whether subjects completed or discontinued from the study will also be presented and the primary reason for discontinuation will be provided for those subjects who withdrew.

9.2 Screening and Baseline Characteristics

9.2.1 Demographics and Baseline characteristics

Descriptive statistics will be used to summarize demographic and baseline variables. Subject demographics include sex, age, ethnicity, race, height, weight, and body mass index (BMI). Age (in years) will be calculated from the date of birth to the date of informed consent. Age will be reported as an integer rounded down. BMI will be calculated using the following formula: BMI $(kg/m^2) = weight (kg)/(height (m))^2$.

All demographic and baseline characteristics will also be listed.

9.2.2 Complete Physical Examination

The Investigator or designee will perform a complete physical examination at screening. Results will be recorded as part of the Medical History. Assessments of height, weight, calculation of BMI, body surface area (BSA), and vital signs will be recorded. Any underlying medical condition will be recorded as ongoing baseline events for future assessment of adverse events or serious adverse events. Only adverse changes from this baseline condition will be considered adverse events.

9.2.3 Medical History

Medical history information will be collected at the Screening visit.

Medical history will be coded using the Medical Dictionary for Regulatory Activities (MedDRA); the dictionary version will be noted in the CSR. Medical history will be summarized

by system organ class and preferred term. Medical history verbatim terms and coded terms will be listed.

Listings will also be provided with the following information:

- History of intractable pain
- Implantation of intrathecal pump and prior opioid use prior to pump implantation
- Surgical intervention(s) for treatment of intractable pain

9.2.4 Prior Concomitant Medications

Prior medications are defined as medications that were taken within 30 days prior to initial dosing with study drug. Concomitant medications are defined as medications taken any time after the start of dosing until the final visit. Medications are also considered concomitant if their stop date is unknown or marked as continuing. Medications with missing start dates will be considered ongoing on the first day of study drug administration except where positive confirmation is available that the medication was stopped before study drug administration.

The World Health Organization Drug Dictionary (WHO-DD) will be used to classify prior and concomitant medications by therapeutic class and preferred term. The WHO-DD version will be noted in the CSR. The number and percentage of subjects receiving concomitant medications will be summarized by Anatomical Therapeutic Chemical (ATC) level 3 and preferred term. Subjects will be counted only once for an ATC class and preferred term, even if the subject took the same medication on multiple occasions. Prior medications will be summarized in a similar manner.

A listing of prior and concomitant medications will also be prepared.

9.2.5 Vital Signs and Electrocardiogram (ECG)

Systolic and diastolic blood pressure, radial pulse, breathing rate and temperature will be obtained at baseline and each study visit and recorded. All vital signs will be obtained in a semi-recumbent position.

A safety electrocardiogram (ECG) will be recorded at Screening or at Baseline for subjects previously enrolled in study in study CNS-HYD201US. The ECG will be used to assess any cardiovascular abnormalities for the purposes of determining eligibility for this trial.

The number and percentage of subjects with normal, abnormal not clinically significant and abnormal clinically significant ECGs will be summarized. ECG results will also be listed.

9.2.6 Clinical Laboratory Assessments

Blood for chemistry, hematology, and urinalysis laboratory tests will be collected at Screening or Baseline for patients previously enrolled in study CNS-HYD201US. The results will be used to determine the subject's eligibility for the study. If abnormal, the investigator will describe the abnormality in the eCRF. Individual laboratory results will not be entered into the eCRF. Abnormal laboratory results will be listed.

Serum pregnancy tests will also be conducted at Screening, Baseline and the Final Visit for women of childbearing potential. Pregnancy test results will be listed

9.3 Study Drug Exposure, Admixtures and Compliance

Dose adjustments and pump refills will be recorded and data listed for each subject. Any admixtures (combination drugs) included into the hydromorphone hydrochloride will be recorded by combination type and dose of each component of the product in the pump and listed for each subject.

9.4 **Protocol Deviations**

Deviations of the protocol will be recorded appropriately. Examples might include, but not necessarily limited to, the following categories:

- Inclusion/exclusion criteria violation
- Prohibited medication use
- Incorrect treatment or dose
- Treatment non-compliance
- Procedure non-compliance
- Safety observation

A listing of major protocol deviations that impact the evaluation of safety will be provided.

9.5 Safety Analyses

Safety will be assessed using the Safety population.

9.5.1 Adverse Events

Unless otherwise noted, analyses will be based on treatment-emergent adverse events (TEAEs), defined as those events that begin or worsen in severity after the first treatment with study drug at Baseline. For AEs with missing start dates, the AE will be considered treatment-emergent unless there is additional information indicating that the AE started prior to the first study drug treatment.

Adverse events will be coded to system organ class and preferred term using MedDRA; the dictionary version will be noted in the CSR. AE severity will be assessed and summarized using

the Common Terminology Criteria for Adverse Events (CTCAE) v 4.03.

AE incidence tables will include the number and percentage of subject reporting at least one AE, as well as, the number and percentage of AEs summarized by MedDRA system organ class and preferred term. Subjects with two or more AEs in the same system organ class will be counted once for that system organ class; likewise for preferred term. For 'by severity' and 'by relationship to study treatment' tables, subjects will be counted once at the maximum severity and at the strongest causal relationship, respectively. Summaries of treatment-related AEs will include those events classified by the investigator as having a possible or probable relationship to study drug (or unknown relationship). Tables will be produced for the following: TEAEs, treatment-related TEAEs, TEAEs by strongest relationship, TEAEs by maximum severity, treatment-emergent serious adverse events (TESAEs), TESAEs by strongest relationship, treatment-related SAEs, and TESAEs by maximum severity. An overall AE summary table will provide top level subject counts for all the AE analyses noted. In addition, the AE summary table will include the number and percentage of subjects reporting any AE (including non TEAEs), the number and percentage of subjects with an AE that led to withdraw of study drug, and the number and percentage of subjects with an AE with outcome of death.

Complete listings of all AEs will be provided (non TEAEs will be flagged with a '*'). In addition, data listings of all SAEs, AEs leading to discontinuation, and AEs leading to death will also be provided.

